4.5. All Subjects who Started Re-Treatment

From all 273 subjects starting the Withdrawal phase after the week 68 visit (randomized subjects only), those 227 subjects will be selected who started re-treatment with open-label guselkumab for additional up to 3 doses after showing PASI deterioration of > 5 until the week 220 visit. In addition, 9 subjects started re-treatment without a Withdrawal phase (among these, 3 subjects who started re-treatment during Study Part 2 (before the week 68 visit) with PASI > 5, and 6 subjects who started re-treatment at the week 68 visit with a PASI value of 3 to 5) and will be included as well. The 236 subjects included in this analysis set will be evaluated for AEs starting from the date of re-treatment until the end of documentation.

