4.2.5. Pharmacokinetics Analysis Set

The PK analysis and the definition of the PK analysis set is out of scope for this SAP.

5. STATISTICAL ANALYSES FOR STUDY PART 3

Description of planned statistical analyses in Study Part 3 will focus on the comparison of the two study groups 3a and 3b which are without administration of study agent in Study Part 3 (ie, group **3a**: randomized to guselkumab 100 mg q8w in Study Part 2 vs. group **3b**: randomized to guselkumab 100 mg q16w in Study Part 2). Inferential statistics (ie, exploratory p-values, confidence intervals, etc.) will be provided only for the week 116/164/220 data of endpoints in Study Part 3.

Note 1: Statistical analysis of Study Part 3 will also include analyses of study data recorded before week 68. Data of Study Parts 1 and 2 will be summarized by descriptive statistics only. No exploratory inferential statistics (ie, p-values, confidence intervals, etc.) will be provided for the data of Study Parts 1 and 2.

Note 2: Subjects of group 3a and 3b who start re-treatment with guselkumab within Study Part 3 (up to week 116) will be evaluated only up to the study visit R0 at which PASI >5 is shown. If PASI was ≥ 3 already at week 68 the subject will not be evaluated for Study Part 3 in the scope of this SAP; a separate SAP will describe the analysis of the re-treatment phase.

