5.1.8. Missing Data Imputation

Data of study endpoints from subjects who started a protocol-prohibited medication/therapy during the study period that could improve psoriasis will be set to 'missing' from that point onward. The protocol-prohibited medications/therapies are listed in section 8.1 of the CSP. For the statistical analysis of Study Part 3, protocol prohibited medication/therapy will be identified in the SDTM DV domain as DVDECOD='RECEIVED DISALLOWED CONCOMITANT TREATMENT'.

After the rule for handling of protocol-prohibited medication/therapy is applied, missing data will be handled as follows:

- Non-responder imputation for binary efficacy endpoints will be applied for subjects with missing data at any study visit.
- Last Observation Carried Forward (LOCF) imputation for continuous efficacy endpoints will be applied for subjects with missing data in Study Part 3.
 - This approach implies that a separate "endpoint" visit will be calculated that gets the imputed value, thus leaving the observed value as it is, if data are summarized descriptively only.
 - The earliest visit used for LOCF approach is the week 68 visit; no data from Parts 1 and 2 will be used as LOCF value for the week 116/164/220 visit.

- Time-to-event analyses of binary endpoints will be performed after the rule for handling of protocol-prohibited medication/therapy is applied (missing data will not be replaced for time-to-event analyses).

An 'observed cases analysis' for all binary and continuous endpoints in Study Part 3 without any imputation of missing data (ie, also not set to missing once protocol-prohibited medication/therapy is started) will also be done. These analyses will provide only descriptive statistical results and will also include by-visit data of Study Parts 1 and 2 (see section 5.6).

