5.4. Major Secondary Endpoint(s) Analysis

Statistical analyses will be descriptive and exploratory only. They will be performed for the Intent-to-treat analysis set and, if requested, the Per-protocol analysis set.

Major secondary endpoints of this study in Study Part 3 are:

- Proportion of subjects with short (≤ 2 years) and longer (>2 years) disease duration who achieve an absolute PASI score of 0, ≤ 1 and <3 at weeks 116, 164, and 220, per study group
- Proportion of subjects who retain disease control (ie, absolute PASI score <3 at all visits) from week 68 through week 116, from week 68 through week 164, and from week 68 through week 220, for subjects with short (≤ 2 years) and longer (>2 years) disease duration per study group.

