5.4.3. Analysis Methods

- Proportion of subjects who achieve an absolute PASI score of 0, ≤ 1 and <3 at weeks 116, 164, and 220
- Proportion of subjects who retain disease control from week 68 through week 116, from week 68 through week 164, and from week 68 through week 220

The proportion of subjects responding to treatment or maintaining disease control will be displayed in frequency tables providing the number and percentage of subjects per study group (NRI and OC analysis) along with odds ratio (OR), relative risk (RR) and risk difference (RD), and two-sided Wald-type 95% confidence intervals (95% CIs) stratified by 'disease duration'. For single proportions within each study group, unstratified two-sided 95% CIs according to Clopper-Pearson will be calculated. Graphical presentation will be presented by means of bar charts.

The two-group large-sample normal approximation Wald Z-test with Mantel-Haenszel stratum weights for 'disease duration' will be used to compare the respective proportion of subjects among the study groups. The Mantel-Haenszel estimate, the two-sided Wald-type 95% confidence limits, and the test for the difference of proportions will be computed by using Mantel-Haenszel stratum weights (Mantel & Haenszel, 1959) and the Sato variance estimator (Sato 1989).

The respective proportion of subjects will also be given by disease duration category (assessed at baseline, ie, ≤ 2 years, >2 years, and additionally only for ≤ 2 years: <15 months, 15 to 24 months) and overall, providing exploratory p-values (unadjusted Chi² test) for the difference between disease duration categories.

Details on handling of missing data are described in section 5.1.8. Subgroup analyses will be performed unstratified for the subgroups as specified in section 5.8.8.

Results will also be given for the entire population. In addition, in a modified OC analysis all subjects fulfilling the criteria for re-treatment within the week 116 visit window (ie, PASI>5) will be disregarded.

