5.7. Safety Analyses

All safety analyses in Study Part 3 will be based on the Safety analysis set. Data from the safety follow-up at week 72 (study groups 2c and 3c) will not be included in the Study Part 3 analyses; last visit to be included for the Study Part 3 analyses is week 116/164/220 or R0 visit in case re-treatment was started. Safety data, including but not limited to, adverse events (AEs), serious AEs, infections, serious infections, and changes in vital signs, will be summarized by study group and overall. AEs will be summarized by Medical Dictionary for Regulatory Activities (MedDRA) system organ class (SOC) and Preferred Terms (PT) for each study group and overall.

For all continuous safety variables, descriptive statistics will include the N, mean, standard deviation, median, quartiles, minimum, and maximum. Categorical variables will be summarized using frequency counts and percentages.

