6.2. Appendix 2 Changes to Protocol-Planned Analyses

No important changes from the planned analyses specified in the protocol and its amendments were applied.

However, the time point of analyses is changed slightly. While the CSP states that “interim analyses are planned after all subjects have completed their visit at week 116 (or at week 144 in case of subjects entering the re-treatment arm in week 116) and at week 164 (or at week 192 in case of subjects entering re-treatment arm in week 164). The final analysis will be performed after all subjects have completed their visit at week 220 (or at week 248 in case of subjects entering the re-treatment arm in week 220)”, it was decided to split the analyses of group 3a/3b subjects and the analyses of group 3c subjects (re-treatment phase). By this, the results for the week 116/164/220 analyses of study groups 3a and 3b will be available as soon as possible. A separate SAP will be written for the analysis of the re-treatment phase that will include – beneath the group 3c – also the analysis of study group 2d (subjects who entered the re-treatment phase already in study part 2).

In addition, some new analyses have been added to the evaluation; see section 5.6 for details.

The initial SAP, prepared before the Dry-run meeting for the first interim analysis (week 116), was updated several times during the course of the study:

- Changes introduced before the Week 116 analysis:
 - The windows for the week 28, 68, 116, 164 and week 220 visits are expanded.
 - For LOCF, the earliest visit used for carrying forward is the week 68 visit.
 - Statistical testing for binary endpoints is also performed for the OC analysis.
 - For binary endpoints, a modified OC analysis is done to exclude visits with PASI>5.
 - Subgroups are compared by statistical testing.
 - The analysis of adverse events excluded AEs starting on the day of the R0 visit.
- Change introduced before the Week 164 analysis:
 - Demographic data are displayed separately for each subgroup.
- Changes introduced before the Week 220 analysis:
 - The subgroups C to H are not evaluated for the analysis of PASI and DLQI response.
 - For the time-to-event endpoints, subgroups I to H are added.
 - All efficacy endpoints (PASI, DLQI, PSSD, BSA, and NAPPA scores and changes from baseline) by visit are presented only for visits with PASI < 5 (OC modified), with subgroups A and B.
 - PASI and DLQI response by visit are evaluated for NRI and OC modified.

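### Part 3 observed-case response rates at weeks 116, 164 and 220 are conditional on not having relapsed and keep values on prohibited therapy, yet the SAP both calls them descriptive only and tests them

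*SAP*

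**What the plan says.** All sections cited are in the Study Part 3 SAP unless stated otherwise.

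- **Main rule (5.1.8).** Data after the start of a prohibited therapy that could improve psoriasis are set to missing. Then: "Non-responder imputation for binary efficacy endpoints will be applied for subjects with missing data at any study visit".
- **OC rule (5.1.8).** An additional analysis without any imputation: "ie, also not set to missing once protocol-prohibited medication/therapy is started) will also be done. These analyses will provide only descriptive statistical results".
- **Reporting of the major secondary endpoints (5.4.3).** Frequency tables are planned "providing the number and percentage of subjects per study group (NRI and OC analysis"), with odds ratio, relative risk, risk difference and 95% intervals. The next paragraph specifies a stratified Wald Z-test. Sections 5.5.3.1 (PASI 75/90/100), 5.5.3.2 (DLQI response) and 5.6 (PASI ≤5) use the same pattern. Section 5.5.3.2 also repeats the disease-duration comparison for OC.
- **Change list (6.2, Appendix 2).** "Statistical testing for binary endpoints is also performed for the OC analysis".
- **Re-treated subjects (opening of Section 5, Note 2).** Subjects of 3a and 3b who start re-treatment "will be evaluated only up to the study visit R0 at which PASI >5 is shown". The note mentions re-treatment up to week 116. The safety section (5.7) states the same cut-off for all three analyses: "last visit to be included for the Study Part 3 analyses is week 116/164/220 or R0 visit in case re-treatment was started". Section 4.2.4 places re-treated subjects in group 3c, outside this SAP.
- **Modified OC (5.4.3, 5.5.3.1, 5.5.3.2, 5.6).** Subjects with PASI >5 in the week 116 window are disregarded. For the final analysis, 5.6 applies the modified version to by-visit PASI and DLQI response at all visits after week 68.
- **Counts (overall-safety SAP, 4.5).** Of 273 subjects entering withdrawal, "those 227 subjects will be selected who started re-treatment with open-label guselkumab" by the week 220 visit.

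**The concern.** Part 3 asks how many super-responders keep control without drug, and whether the earlier dosing interval or disease duration matters. A subject leaves that state by losing control (PASI >5, then re-treatment) or by starting another antipsoriatic therapy. At a fixed week, OC treats neither exit as a failure.

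A subject re-treated before the time point has no later 3a/3b value and drops out of the denominator, although the outcome is a known loss of control. A subject on prohibited therapy stays in, and a PASI <3 reached on that therapy counts as response. Protocol 11.3 classes starting such a therapy as treatment failure. Protocol 8 and 9.1.5 have these subjects still complete week 220, so such values can arise.

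The OC contrasts of 3a with 3b, and of short with longer disease duration, therefore compare subjects selected on the outcome under study. Descriptive tables with a clear label would carry little risk. Intervals and nominal p-values invite the reader to treat the contrasts as comparisons of the randomized groups. The SAP's two statements on whether inference is done cannot both be programmed.

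**Working it through.** **1. The plan's own counts.** Overall-safety SAP 4.5: 227 re-treated after withdrawal, plus 9 without a withdrawal phase (3 during Part 2 and 6 at week 68). 3 + 6 = 9 and 227 + 9 = 236, as stated there.

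**2. Who is left at week 220.** 227/273 = 83.2% re-treated; 273 − 227 = 46, and 46/273 = 16.8%.

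**3. OC against NRI.** Let k be the number with PASI <3 at week 220 and D the number with a week 220 value. NRI = k/273, OC = k/D, and the ratio is 273/D. With D = 46 the ratio is 5.9. The documents do not give k, so a range is assumed:

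| k (assumed) | NRI, k/273 | OC, k/46 |
|---|---|---|
| 10 | 3.7% | 21.7% |
| 20 | 7.3% | 43.5% |
| 30 | 11.0% | 65.2% |
| 40 | 14.7% | 87.0% |

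D is only approximately 46. Subjects whose first re-treatment visit (R0) is the week 220 visit are observed there with PASI >5 and add to D. With 10 or 20 of them (assumed) and k = 30, OC is 30/56 = 53.6% or 30/66 = 45.5%, and the ratio is 4.9 or 4.1. Earlier study exits, including those at week 116 under the unamended protocol (5.2), reduce D. With 40 observed (assumed), OC is 30/40 = 75.0%, but the step from 46 to 40 reflects other missingness, not relapse.

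**4. Values on prohibited therapy.** Suppose m of k = 30 are controlled only on prohibited therapy (m assumed):

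| m | OC as defined, 30/46 | OC with the rule applied, (30−m)/(46−m) | NRI, (30−m)/273 |
|---|---|---|---|
| 0 | 65.2% | 65.2% | 11.0% |
| 3 | 65.2% | 62.8% | 9.9% |
| 5 | 65.2% | 61.0% | 9.2% |
| 10 | 65.2% | 55.6% | 7.3% |

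OC as defined does not respond to m at all. The time-to-event analyses in the same SAP are also described as observed cases, but only after the prohibited-therapy rule (5.5.3.1), so the term has two meanings.

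**5. Effect on a comparison.** Three assumed splits of 273 into 137 and 136, each with 46 not re-treated in total (unstratified Wald test):

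| Not re-treated | PASI <3 | NRI difference (p) | OC difference (p) |
|---|---|---|---|
| 27 vs 19 | 20 vs 14 | +4.3 points (0.28) | +0.4 points (0.98) |
| 31 vs 15 | 22 vs 11 | +8.0 points (0.042) | −2.4 points (0.87) |
| 33 vs 13 | 24 vs 10 | +10.2 points (0.010) | −4.2 points (0.76) |

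A difference that arises through relapse can disappear or change sign under OC.

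**6. Modified OC.** It removes PASI >5 at the time point as well. At week 116 the added endpoint PASI ≤5 (5.6) is then 100% in both groups by construction.

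**7. Descriptive or tested.** Section 5.1.8 says descriptive only. Section 5.4.3 names OC beside the ratios and intervals; its test paragraph does not name OC. Section 5.5.3.2 does name OC for a comparison, on DLQI. Appendix 2 states testing for binary endpoints generally. Sections 5.4.3, 5.5.3.2 and Appendix 2 point one way, and 5.1.8 was not brought into line.

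**The case against.** The best defence is that the right estimate is already planned. NRI after the prohibited-therapy rule counts both kinds of exit as non-response. Kaplan-Meier and Cox analyses of time to loss of control count PASI >5 as an event and also apply the rule first. Subgroup analyses of binary endpoints use NRI (5.8.8). Part 3 is exploratory with nominal p-values (5.1), and the protocol lists OC only as an option (11.11). Attrition is visible: tables give counts, disposition is reported (5.2), and 5.6 adds re-treatment starts by period and disease duration. Appendix 2 records OC testing as a deliberate change, so the sentence in 5.1.8 may simply be out of date.

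All of this stands, and it limits the point to a supportive analysis. It does not make the OC contrasts interpretable, nor settle which section governs.

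A reader might infer more than the documents support:

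- **That OC removes known failures from the endpoint that measures drug-free control most directly**, "Proportion of subjects who retain disease control (ie, absolute PASI score <3 at all visits) from week 68 through week 116" (and through weeks 164 and 220). The SAP does not say so. A PASI >5 at R0 is an observed failure of that endpoint, and an analysis without imputation need not drop it. The text is silent.
- **That prohibited therapy inflates OC materially.** No count of users is given; it could be zero. Protocol 4.2 also bars earlier users of prohibited antipsoriatic medication from continuing after week 116, in its note on subjects rejoining for the extension.
- **That OC rates such as 65% or 75% are trial results.** They are illustrations on assumed k and D.

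**Conclusion.** The point holds for the fixed-week response endpoints: PASI 0, ≤1 and <3, and likewise PASI ≤5, PASI 75/90/100 and DLQI response, at weeks 116, 164 and 220. For these, OC omits subjects re-treated earlier for PASI >5 and keeps values on prohibited therapy, and modified OC also omits PASI >5 at the visit. The SAP contradicts itself on whether OC carries inference.

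The firm figures are 227 of 273 re-treated and 46 (16.8%) not. The factor of about 5.9 assumes that all 46 are observed, that no R0 falls at week 220, and that the same responders are counted in both rates. Responder counts, the split between groups and the number on prohibited therapy are assumptions.

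The documents do not support a conclusion that the Part 3 findings as a whole are unsound, because NRI and the time-to-event analyses handle both exits. This should be corrected, but it does not touch the confirmatory result of Part 2.

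**What to change.** Reconcile 5.1.8 with 5.4.3, 5.5.3.2 and Appendix 2 by choosing one of two routes:

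- **(a) Keep OC inference on a defined version.** For OC tests and intervals, count subjects re-treated for PASI >5 before the time point as observed non-responders, do not accept values after the start of prohibited therapy as response, and omit only visits missing without such an explanation.
- **(b) Keep OC and modified OC purely descriptive.** Label them 'among subjects not yet re-treated', show n, apply the prohibited-therapy rule, and remove p-values, ratios and intervals.

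Under either route, state for PASI <3 at all visits that an observed PASI >5 at R0 is a failure in every version of the analysis.

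The cost is SAP wording and a re-run of existing tables, using the re-treatment date and the deviation flag already in the data. OC rates become less favourable under (a). The overall-safety SAP of April 2025 describes the Part 3 analyses as already performed, so changed tables would be a revision made after results were available and should be marked as such.

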5.2. Participant Dispositions

The number of subjects in the following disposition categories will be summarized throughout the study for Study Part 3 by study groups (ie, groups **3a**, **3b**) and the total of group **3a** and **3b**:

- Subjects who entered groups 3a or 3b of Study Part 3 (without those subjects who started re-treatment already at the week 68 visit)
- Subjects of groups 3a and 3b who completed Study Part 3 until the week 116/164/220 visit
- Subjects of groups 3a and 3b who discontinued Study Part 3 prematurely until the week 116/164/220 visit, respectively
- Subjects of groups 3a and 3b who started re-treatment at the week 116 visit
- Subjects of groups 3a and 3b who were still in the Withdrawal period at the week 116 visit
- Subjects of groups 3a and 3b who terminated Study Part 3 at the week 116 visit according to the unamended study protocol **
- Subjects of groups 3a and 3b who continued the Withdrawal phase beyond the week 116 visit
- Reasons for termination of study within Study Part 3 (subjects of groups 3a and 3b).

** For this subset of subjects, summary and frequency tables will be created showing age at baseline, sex, disease duration, as well as PASI and DLQI values at week 116.

5.3. Primary Endpoint(s) Analysis

Not applicable for the Study Part 3 analysis.

5.3.1. Definition of Endpoint(s)

Not applicable for the Study Part 3 analysis.

5.3.2. Estimand

Not applicable for the Study Part 3 analysis.

5.3.3. Analysis Methods

Not applicable for the Study Part 3 analysis.

5.4. Major Secondary Endpoint(s) Analysis

Statistical analyses will be descriptive and exploratory only. They will be performed for the Intent-to-treat analysis set and, if requested, the Per-protocol analysis set.

Major secondary endpoints of this study in Study Part 3 are:

- Proportion of subjects with short (≤ 2 years) and longer (>2 years) disease duration who achieve an absolute PASI score of 0, ≤ 1 and <3 at weeks 116, 164, and 220, per study group
- Proportion of subjects who retain disease control (ie, absolute PASI score <3 at all visits) from week 68 through week 116, from week 68 through week 164, and from week 68 through week 220, for subjects with short (≤ 2 years) and longer (>2 years) disease duration per study group.

5.4.1. Definition of Endpoint(s)

5.4.1.1. Psoriasis Area and Severity Index (PASI)

The Psoriasis Area and Severity Index (PASI) is an instrument used for assessing and grading the severity of psoriatic lesions and their response to therapy. In the PASI system, the body is divided into 4 regions: the head, trunk, upper extremities, and lower extremities. Each of these areas is assessed separately for erythema, induration and scaling, which are each rated on a scale of 0 to 4. The PASI produces a numeric score that can range from 0 (no psoriasis) to 72. A higher score indicates more severe disease.

5.4.2. Estimand(s)

NA

5.4.3. Analysis Methods

- Proportion of subjects who achieve an absolute PASI score of 0, ≤ 1 and <3 at weeks 116, 164, and 220
- Proportion of subjects who retain disease control from week 68 through week 116, from week 68 through week 164, and from week 68 through week 220

The proportion of subjects responding to treatment or maintaining disease control will be displayed in frequency tables providing the number and percentage of subjects per study group (NRI and OC analysis) along with odds ratio (OR), relative risk (RR) and risk difference (RD), and two-sided Wald-type 95% confidence intervals (95% CIs) stratified by 'disease duration'. For single proportions within each study group, unstratified two-sided 95% CIs according to Clopper-Pearson will be calculated. Graphical presentation will be presented by means of bar charts.

The two-group large-sample normal approximation Wald Z-test with Mantel-Haenszel stratum weights for 'disease duration' will be used to compare the respective proportion of subjects among the study groups. The Mantel-Haenszel estimate, the two-sided Wald-type 95% confidence limits, and the test for the difference of proportions will be computed by using Mantel-Haenszel stratum weights (Mantel & Haenszel, 1959) and the Sato variance estimator (Sato 1989).

The respective proportion of subjects will also be given by disease duration category (assessed at baseline, ie, ≤ 2 years, >2 years, and additionally only for ≤ 2 years: <15 months, 15 to 24 months) and overall, providing exploratory p-values (unadjusted Chi² test) for the difference between disease duration categories.

Details on handling of missing data are described in section 5.1.8. Subgroup analyses will be performed unstratified for the subgroups as specified in section 5.8.8.

Results will also be given for the entire population. In addition, in a modified OC analysis all subjects fulfilling the criteria for re-treatment within the week 116 visit window (ie, PASI>5) will be disregarded.

